"Impact of melatonin, food timing and receptor gene variant on type 2 diabetes risk"

Main researcher: [name]

Identifier: NCT03036592

Date: 09/01/2016

Impact of melatonin, food timing and receptor gene variant on type 2 diabetes risk

INCLUSION/EXCLUSION CRITERIA

- 18-65 years
- BMI >18,5 kg/m² and <40 kg/m²
- No diabetics, no cancer
- No pregnant
- European race
- If your work is outside of the range between 7:00 a.m. and 11:00 p.m. In the case that the patients have been shift worker, they will can participate if they leave the shift during 2 years.
- Not take melatonin in the last two weeks, and the two weeks of the study
- Not eat the following drugs:

I. Those that affect blood sugar values: a) insulin; b) medications for type 2 diabetes such as Metformin or other oral antidiabetics such as sulfonylureas, meglitinides, or glitazones; c) Corticosteroids / steroids; d) growth hormone

II. Those that affect blood clotting: e) anticoagulant drugs, or anticoagulants such as heparin, warfarin (Coumadin) or copylores (Plavix)

III. Those that affect the values of melatonin or sleep and circadian rhythms: f) beta-blockers for hypertension (high blood pressure), such as metoprolol (Lopressor), mexiletine, propranolol or verapamil; g) medications for sleep disorders (circadian rhythms) such as lithium, ramelteon, hypnotics (such as Ambien, Sonata or Lunesta) or other stimulants such as Provigil

Name if you take medicines such as nonsteroidal, anti-inflammatory drugs such as ibuprofen or aspirin

• History (family history questions) to non-patients [name]

Level of studies: school / institute / university

If you are a smoker, how many cigarettes / day

MEASUREMENTS

1. Food timing and dietary record:

- 7 consecutive days dietary food intake (mobile app and foods pictures)
- 2. Light exposure: HOBO pendant sensor (7 consecutive days included those days of the study). The day of the study, be sure that during OGTT (Oral Glucose Tolerance Test) in the late condition (1 hour before their habitual bedtime) the light not be more than 10 luxes and that this situation star 30 minutes before the time of the OGTT. In the early condition (4 hour before their habitual bedtime) the light would be more than 500 luxes.

3. Anthropometric and biochemistry measurements:

- BMI
- Waist and Hip (cm).
- Impedance data: % Fatty Mass, Kg Fatty Weight, Kg Lean Mass, Kg Muscle Mass, Kg Total Water, % Total Water, Kg Bone Mass, Basal Metabolism (KJ), Basal Metabolism (Kcal), Metabolic Age, Visceral Fat Level, Degree of Obesity (%)
- Sex, age
- Menopause (Yes/No) and the date of the last menstruation. The patient should be pipi before the impedance, all of the impedances would be at the same time (19:00-20:00h).

4. Questionnaires:

- 1) Demographics and Health Survey: socioeconomic status, habitual alcohol intake, smoking, sleep apnea, insomnia
- 2) Inform consent
- 3) Anthropometric characteristics and OGTT conditions
- 4) International Physical Activity Questionnaire (IPAQ)
- 5) Morningness Eveningness Questionnaire (MEQ)

- Impact of melatonin, food timing and receptor gene variant on type 2 diabetes risk
- 6) Emotional Eating Questionnaire (EEQ)
- 7) Food and Sleep log (food and timing)
- 8) Pittsburgh Sleep Quality Index
- 9) Day of the experiment menu
- 10) Control sheet
- 11) Insomnia Severity Index (ISI)
- 12) Patient Health Questionnaire-9 (PHQ-9)

5. Actigraphy

Actigraphy (sensor). For 7 consecutive days to record the activity rhythm the week before the OGTT. It should be the week before the study to know how is melatonin (although if you cannot it could be two weeks before)

6. OGTTs

We will administer 75 grams of glucose to the subject after the basal measurement in both conditions. Fisher Scientific; Fisher brand Glucose Tolerance Test Beverage, 75 g (75 Sun-dex); Orange flavored, caffeine free, non-carbonated; 10 oz fluid / 296 ml.

Link: https://www.fishersci.com/shop/products/fisherbrand-glucose-tolerance-test-beverages-9/401223fb

Write the time of each extraction

No more than 2 minutes in drink the glucose

8-h fasting

2 measures or conditions:

- 4 h before their habitual bedtime.
- 1 h before their habitual bedtime (should come 1h before of the T0 and keep in the dark). The samples will be just before the glucose T0 and at T30', T60', T 90'y T120' minutes after the glucose.
- Serum insulin and glucose.

7. Determinations

- Glucose and insulin in the 5 times (T0, T30', T60', T 90'y T120')
- Melatonin in T0' and T120'

8. Subjects report

- 1) Demographics and Health Survey: socioeconomic status, habitual alcohol intake, smoking, sleep apnea, insomnia
- 2) Inform consent
- 3) Anthropometric characteristics and OGTT conditions
- 4) International Physical Activity Questionnaire (IPAQ)
- 5) Morningness Eveningness Questionnaire (MEQ)
- 6) Emotional Eating Questionnaire (EEQ)
- 7) Food and Sleep log (food and timing)
- 8) Pittsburgh Sleep Quality Index
- 9) Day of the experiment menu
- 10) Control sheet
- 11) Insomnia Severity Index (ISI)
- 12) Patient Health Questionnaire-9 (PHQ-9)

11. Store aliquots:

-Glucose: 30-400 μl -Insulin: 30-400 μl -Melatonin: 30-400 μl

INTERVENTION STUDY PROTOCOL

Impact of melatonin, food timing and receptor gene variant on type 2 diabetes risk

-Serum: 400 μl -DNA: 200 μl

200-300 μ l: 1 for insulin, 1 for melatonin 1 for glucose, and the rest for store in the freezer.

"Impact of melatonin, food timing and receptor gene variant on type 2 diabetes risk"

Main researcher: [name]

Identifier: NCT03036592

Date: 09/01/2016

EXCLUSION CRITERIA

-Age between 18 and 70 years.
-No diabetes.
-Without any relevant medication use such as:

Diabetes-related medications
Growth hormones
Anti-coagulants
Beta-blockers
Hypnotics
Melatonin use or other sleep-related medications.

MEASUREMENTS

1. Habitual dinner timing:

In order to evaluate food habits, initial dietary intake will be determined by a 24-hour dietary recall in both populations at the initial screening. A smartphone application that transmits a time-stamp and photograph of each snack/meal taken during the 7 days and nights prior to the tests was used. This was supplemented with a 7-day food record.

2. Light exposure:

Light exposure was measured during the start of the early and late evening OGTTs. For the late evening OGTT, light intensity will be kept dim (0-25 lux), and for the early evening OGTT, light intensity will be kept bright ((\geq 450 lux).

3. Other traits:

- BMI
- Waist and Hip (cm)
- Sex, age

4. Melatonin at time of OGTT early and late:

Plasma melatonin will be measured 4 times per subjects at T0 and T120 during both OGTTs (2-time points x 2 OGTT) at the same laboratory by radioimmunoassay (RIA) (IBL, Germany). The intra- and inter-assay precision was 6.7% and 10.4% respectively.

5. Behavioral characteristics:

Physical activity will be assessed by the International Physical Activity Questionnaire (IPAQ) which determines physical activity over the last 7 days. Habitual weekday and weekend sleep timing and duration will be estimated by questionnaire and supplemented by 7-days of smartphone application.

6. OGTTs

A 75g OGTT will be performed twice on 750 participants, once in the early and once in the late evening. After an 8 hour fast, blood samples will be collected to measure glucose and insulin at 0 (fasting) and 30, 60, 90 and 120 minutes will be measured. Glucose will be measured using the Gluco-quant hexokinase test, COBAS Integra 400 (Roche, Indianapolis, IN) with a sensitivity of 2mg/dL and an intra- and interassay precision of 1.0% and 1.7%. Insulin was measured using the ECLIA ELECSYS test, COBAS e-801 (Roche Diagnostics GmbH, Mannheim, Germany) with a sensitivity of 0.2 ulU/ml and an intra- and interassay precision of 0.8-1.5% and 3.2-3.7%.

- 2 measures or conditions:
- Early: 4 h before their habitual bedtime.
- Late: 1 h before their habitual bedtime (should come 1h before of the T0 and kept in the dim light condition). The samples will be just before the glucose T0 and at T30', T60', T 90'y T120' minutes after the glucose.

7. Biochemical determinations

- Glucose and insulin in the 5 times (T0, T30', T60', T 90'y T120')
- Melatonin in T0' and T120'

8. Statistical analysis plan

Postprandial glucose and insulin responses were estimated during the 120 minutes using incremental area under-the-curve (AUC) and were calculated by the trapezoidal method. An ANOVA of repeated measurements (ANOVArm) was used to compare glucose and insulin responses between early and late eating conditions. If significant, paired t-tests were performed to examine statistical significance between each OGTT time point. Insulin sensitivity was evaluated using the insulin sensitivity index (ISI) calculated from the OGTT data as 10,000/ (fasting glucose × fasting insulin × mean OGTT glucose × mean OGTT insulin)^{1/2}. Beta-cell function was assessed as the corrected insulin response (CIR) during the OGTT (100 × insulin30/ [glucose30 × (glucose30 – 3.89)]). Finally, the disposition index (DI) was calculated as a measure of insulin secretion in relation to insulin sensitivity (DI= ISI×CIR). Paired t-tests were performed to compare metrices in the two conditions.

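### Neither document says how the order of the early and late OGTTs is allocated, and SAP section 8 names no period term, so unequal orders could mix timing with visit

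*SAP*

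**What the plan says.** SAP section 6 sets a within-person design: "A 75g OGTT will be performed twice on 750 participants, once in the early and once in the late evening". Section 6 of both documents defines the two conditions only by time before habitual bedtime, 4 hours for early and 1 hour for late, with an 8-hour fast. Neither says which condition is tested first, or whether order is randomised, balanced, fixed or left to convenience.

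SAP section 8 describes three kinds of test:

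- for the glucose and insulin responses, "An ANOVA of repeated measurements (ANOVArm) was used to compare glucose and insulin responses between early and late eating conditions";
- for individual time points, "If significant, paired t-tests were performed to examine statistical significance between each OGTT time point";
- for the derived indices (insulin sensitivity index ISI, corrected insulin response CIR, disposition index DI), "Paired t-tests were performed to compare metrices in the two conditions".

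No period, visit or order term is named for any of them. The SAP does not list the factors of the ANOVA at all, so for that model the accurate statement is that no such term is named. The paired t-tests as described contain none.

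**The concern.** The early-late contrast is the only comparison that SAP section 8 tests. In a two-condition within-person design it is protected against a difference between first and second visits only if the two orders are balanced or if period is in the analysis. The plan provides for neither. If results at a second OGTT differ from those at a first for any reason unrelated to time of day, and one order is more common, part of that difference is counted as an effect of timing.

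The distortion can create an apparent timing effect or hide a real one, depending on the sign of the visit effect and on which order predominates. If everyone is tested in the same order, timing and visit are completely confounded and no later analysis can separate them.

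**Working it through.** **Are there really two visits?** On any one evening the early test starts 3 hours before the late one (4 h - 1 h). A late test that evening would start 3 hours after a 75 g glucose load, not after an 8-hour fast. The tests therefore fall on different days, and every participant has a first and a second visit.

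**Inputs.** From the documents: n = 750 pairs (SAP section 6). The SAP gives no alpha, power, effect size or SD behind 750, so that figure cannot be reproduced; it is used here only as the number of pairs. Assumed: two-sided alpha 0.05; visit effect d of 0.05 or 0.10, in SDs of the within-person difference; order split p; no true timing effect; no differential carryover.

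**Bias.** Let τ be the true late-minus-early difference, π the second-minus-first visit effect, and p the share tested early first.

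- Early first: expected late-minus-early difference = τ + π
- Late first: τ - π
- Overall: p(τ + π) + (1 - p)(τ - π) = τ + (2p - 1)π

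The bias is zero if π = 0 or p = 0.5.

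**Scale.** The standard error of the mean difference is 1/√750 = 0.037 SD. The difference detectable with 80% power is (1.960 + 0.842)/√750 = 0.102 SD.

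**False-positive rate.** Noncentral t, 749 df, noncentrality (2p - 1) × d × √750, with √750 = 27.39.

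| Order split | 2p - 1 | Bias, d = 0.05 | Noncentrality | Rate | Bias, d = 0.10 | Noncentrality | Rate |
|---|---|---|---|---|---|---|---|
| 50:50 | 0 | 0 | 0 | 5.0% | 0 | 0 | 5.0% |
| 60:40 | 0.2 | 0.010 | 0.27 | 5.9% | 0.020 | 0.55 | 8.5% |
| 75:25 | 0.5 | 0.025 | 0.68 | 10.5% | 0.050 | 1.37 | 27.7% |
| 100:0 | 1.0 | 0.050 | 1.37 | 27.7% | 0.100 | 2.74 | 78.1% |

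**Does the adjustment work?** The period-adjusted estimate is the unweighted mean of the two order groups' mean late-minus-early differences: [(τ + π) + (τ - π)]/2 = τ. Simulation with 5,000 runs per setting, d = 0.10 and τ = 0:

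- 60:40: plain paired test rejects in 8.5%, adjusted in 4.8%.
- 75:25: plain test has bias 0.049 and rejects in 27.4%; adjusted has bias of about 0 and rejects in 5.2%.
- 100:0: plain test rejects in 78.2%; the adjusted estimate cannot be computed.

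Under simple randomisation of order, the plain paired test rejects in 4.9% (20,000 runs) at d = 0.10 and at d = 0.20.

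**Price of adjusting.** The standard error is multiplied by 1/√[4p(1 - p)]: 1.00 at 50:50, 1/√0.96 = 1.02 at 60:40, and 1/√0.75 = 1.15 at 75:25.

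**The case against.** The harm is doubly conditional: it needs both a visit effect and unequal orders, and the documents give evidence of neither. These are very short documents, and silence does not show that order was uncontrolled. The protocol lists a control sheet and a form for OGTT conditions, which may record it. All of this stands. A reader might infer that order was fixed or that the contrast is in fact biased; the text supports neither. It shows only that the plan does not exclude these outcomes. One sentence would settle the matter if order was randomised.

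It is also fair that the rates look high partly because 750 pairs make small differences significant. At 75:25 the bias is at most 0.05 SD under the assumptions used, about half of the 0.102 SD detectable with 80% power. Under a single order with a 0.10 SD visit effect it is about equal to that detectable difference.

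A reader might infer that the missing period term is an error in itself. It is not: once order is randomised, the plain paired test holds its level. The term matters most where order was not randomised.

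A reader might also apply the tabulated rates to every outcome. They hold for a single paired difference. Rates for the ANOVA interaction or for incremental AUC would depend on how a visit effect varies over the five time points and on variances that the documents do not give, so none are claimed.

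Finally, section 8 is written in the past tense, so randomisation may come too late for some or all participants. The fix allows for that.

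**Conclusion.** The omission is certain; its consequence is conditional. Neither document allocates the order of the two OGTTs, and SAP section 8 names no term that would deal with an unequal order. The plan as written permits anything from a balanced design to one in which timing and visit are fully confounded.

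The harm runs from nil (no visit effect, or balanced orders) to serious (a single order), as tabulated above. This rests on assumed visit effects and order splits, two-sided 0.05 testing and no differential carryover. The sign of any bias is unknown. The point should be fixed because the remedy is cheap and the worst case cannot be repaired afterwards, not because bias has been shown.

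**What to change.** **Section 6 of both documents.** Add, for example: *Participants not yet tested are randomised 1:1 to early-first or late-first; the order and date of each OGTT are recorded.* This is the main step.

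**SAP section 8.** Include period in the repeated-measures model. Use the period-adjusted paired comparison (the mean of the two order groups' mean late-minus-early differences) for the time points, incremental AUC, ISI, CIR and DI. State that it assumes no differential carryover.

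**Participants already tested.** Report the order split. If both orders occurred, apply the period adjustment. If only one did, state that timing and visit order cannot be separated.

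**Cost.** A randomisation list, one recorded variable and one degree of freedom per paired comparison (748 instead of 749). No visits or participants are added. The standard error is unchanged at 50:50, 2% wider at 60:40 and 15% wider at 75:25.

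### The repeated-measures ANOVA that gates the time-point tests has no stated factors, sphericity correction or missed-draw rule; a mixed model on all observed draws would serve better

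*SAP*

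**What the plan says.** SAP section 6 sets the design: "A 75g OGTT will be performed twice on 750 participants, once in the early and once in the late evening". SAP section 7 lists "Glucose and insulin in the 5 times (T0, T30', T60', T 90'y T120"), so each participant contributes 5 × 2 = 10 values per analyte.

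SAP section 8 first defines the response: "Postprandial glucose and insulin responses were estimated during the 120 minutes using incremental area under-the-curve (AUC"). The next sentence names the early/late test: "An ANOVA of repeated measurements (ANOVArm) was used to compare glucose and insulin responses between early and late eating conditions". The one after makes that test a gate: "If significant, paired t-tests were performed to examine statistical significance between each OGTT time point". The insulin sensitivity index (ISI), corrected insulin response (CIR) and disposition index (DI) are handled separately: "Paired t-tests were performed to compare metrices in the two conditions".

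Neither document states the ANOVA factors, a condition-by-time term, a sphericity check or correction, an analysis set, an alpha level, or what happens to a participant with a missed draw.

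**The concern.** The ANOVA carries the early/late comparison of glucose and insulin and decides whether the time-point tests are run, so its behaviour with incomplete data matters.

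In its classical form, a two-way repeated-measures ANOVA needs a full set of values from each person. With ten draws, a low loss rate per draw becomes a noticeable loss of participants, including all the samples they did give.

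Lost draws in the late session are foreseeable. SAP section 6 places it as "Late: 1 h before their habitual bedtime", so the T90 and T120 samples fall 30 and 60 minutes after habitual bedtime. The early session starts 4 h before bedtime and ends 2 h before it.

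Separately, the classical F test for condition-by-time assumes sphericity, which serial glucose and insulin values are unlikely to satisfy. At stake are power, possible bias if late draws are lost in a way tied to that session's glucose, and the error rate of one of the tests that might serve as the gate.

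**Working it through.** **Inputs from the documents.** 750 participants (SAP section 6) and 10 draws per analyte (SAP sections 6 and 7). The 750 cannot be reproduced, because no alpha, power, effect size, SD or dropout allowance is given.

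**Assumptions.** Two-sided alpha 0.05; an effect with 80% power at 750; loss rate *m* per draw, independent across draws. The documents give no loss rate, so a range is shown.

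**1. Effect size.** d = (1.960 + 0.842)/√750 = 2.802/27.386 = 0.1023.

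**2. Complete cases.** n = 750(1 − m)^10 and power = Φ(d√n − 1.960). At m = 2%: 0.98^10 = 0.8171; n = 612.8; 0.1023 × √612.8 − 1.960 = 0.572; Φ = 0.716.

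**3. Observed pairs kept.** Pairs at a given time point = 750(1 − m)^2. At m = 2%: 720.3 pairs; 0.1023 × √720.3 − 1.960 = 0.786; Φ = 0.784.

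| m per draw | Complete cases | Power | Pairs per time point | Power |
|---|---|---|---|---|
| 0.5% | 713 | 78% | 743 | 80% |
| 1% | 678 | 76% | 735 | 79% |
| 2% | 613 | 72% | 720 | 78% |
| 5% | 449 | 58% | 677 | 76% |

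**4. Clustered loss.** If draws are lost by whole session at 2% per session, 750 × 0.98² = 720 participants stay complete, not 613. A mixed model then recovers little, because nothing is observed from the missed session.

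**5. Sphericity.** The condition-by-time test has (2 − 1)(5 − 1) = 4 df. It depends on the covariance of the late-minus-early differences across the five times. Simulated type I error at n = 750, 10,000 runs per pattern:
- Compound symmetry (sphericity holds): 5.0%.
- First-order autoregressive, equal variances, adjacent correlation 0.5, 0.7, 0.8: 6.3%, 7.1%, 7.7%.
- Adjacent correlation 0.7 with smaller fasting variance, two patterns: 7.2% and 7.9%.
- With Greenhouse-Geisser, these five autoregressive patterns gave 4.9 to 5.2%.

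Widening the adjacent correlation to 0.3–0.9 (epsilon 0.92 to 0.58) gave 5.5 to 7.9% uncorrected. The theoretical worst case (epsilon 0.25) is about 12.4%.

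**6. Bias.** In a simulated glucose example with a true mean difference of 0.398 mmol/L, complete-case estimates were:
- Loss completely at random: 0.398.
- Loss driven by the participant's overall glucose: 0.398.
- Late T120 lost more often when late T90 is high, weaker and stronger dependence: 0.371 and 0.334. These are (0.398 − 0.371)/0.398 = 7% and (0.398 − 0.334)/0.398 = 16% low.

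**7. Choice of covariance.** A mixed model with participant and session-within-participant effects was tested on complete data (n = 750, time correlation 0.7^lag, session correlation multiplied across times). Two sets of simulations gave condition-by-time type I error of 6.9 and 7.1% at session correlation 0, 2.3 and 2.1% at 0.3, and 0.6 and 0.75% at 0.5. That structure forces equal covariance within a session, so it does not remove the sphericity problem.

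**The case against.** The strongest reply is that the SAP is silent rather than wrong. A reader might infer that it discards both sessions after one missed draw and uses an uncorrected F test. It says neither: these are the usual properties of the named method, and a Greenhouse-Geisser correction is compatible with the wording. That stands, so the point is conditional on the classical form.

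Second, the sentence before the ANOVA defines responses as incremental AUC. On that reading there are two levels, F equals t squared, and sphericity cannot arise. This also stands as a possible reading. The time-point follow-up favours the 2 × 5 layout, and on the AUC reading a missed draw still prevents the planned five-point AUC.

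Third, a reader might infer that sphericity inflates the early/late test itself. It does not: the main effect has 1 df. The paired t-tests, including those of ISI, CIR and DI, are also unaffected.

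Fourth, a reader might infer that heavier loss in the late session is enough to bias the contrast. It is not: draws lost because of the hour, unrelated to glucose or insulin values, cost precision only. The documents suggest no route from a participant's glucose during the session to a missed draw, so the 7% and 16% are illustrations.

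Finally, the power figures rest on assumed rates and independence. At 0.5 to 1% loss, power drops only from 80% to 78–76%. That is a modest cost, but an avoidable one.

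**Conclusion.** The point holds as a conditional weakness in the specification, with a better method available at little cost. SAP section 8 leaves the factors, the sphericity correction and the handling of missed draws open for its gating test. If the test is the classical 2 × 5 ANOVA, the cost runs from negligible to serious with the loss rate: 2 percentage points of power at 0.5% independent loss per draw, 22 points at 5%. Keeping observed pairs holds the loss to about 4 points even at 5%. Clustered loss narrows this advantage.

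The error-rate problem is confined to an uncorrected condition-by-time test, at roughly 5.5 to 8% under plausible serial correlation. Bias is possible but not shown. The loss rates, covariance patterns and glucose profiles are all assumptions; only the 750 and the ten draws come from the documents.

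**What to change.** In SAP section 8:

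- Analyse each analyte with a linear mixed model on all observed draws: fixed condition, time and condition-by-time; unstructured 10 × 10 within-person covariance (10 × 11/2 = 55 parameters, for a planned 750 participants); REML with Kenward-Roger degrees of freedom.
- Do not substitute a participant plus session-within-participant covariance.
- Name the gate test, and take it and the time-point contrasts from this model.
- If the repeated-measures ANOVA is kept as a sensitivity analysis, state its factors and report the Greenhouse-Geisser p-value.
- Add a separate missed-draw rule for AUC, ISI, CIR and DI. The mixed model does not resolve these: five-point AUC and ISI need the full session, CIR needs the T30 samples, and DI needs both ISI and CIR.

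The cost is SAP wording and slightly more programming. No new data are needed, and with complete data the estimated condition effect is essentially unchanged.

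### SAP section 8 follows a significant ANOVA with up to ten unadjusted time-point t-tests; once a real difference exists at one time, the ANOVA no longer protects the others

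*SAP*

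**What the plan says.** SAP section 8 sets out two steps. The first is an omnibus comparison: "An ANOVA of repeated measurements (ANOVArm) was used to compare glucose and insulin responses between early and late eating conditions". The second depends on it: "If significant, paired t-tests were performed to examine statistical significance between each OGTT time point".

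SAP section 7 fixes the sampling times for both analytes: "Glucose and insulin in the 5 times (T0, T30', T60', T 90'y T120". SAP section 6 gives the size and the pairing: "A 75g OGTT will be performed twice on 750 participants, once in the early and once in the late evening".

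Read naturally, the second step is an early-versus-late paired t-test at each of five times, done for glucose and again for insulin: 5 × 2 = 10 tests if both ANOVAs are significant. Neither document states a significance level, a multiplicity adjustment, which ANOVA effect (condition, time or condition-by-time) must be significant, or whether the time-point tests are confirmatory or exploratory.

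**The concern.** A preliminary omnibus test gives weak control of error. It keeps false time-point claims rare when the two sessions differ nowhere, because the t-tests are then seldom reached. It does nothing for the null time points once a real difference at another time has made it significant. The study is set up to look for a late-versus-early difference, and with 750 pairs even a difference confined to one time will usually pass the first step.

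What is at stake is any statement about when in the glucose tolerance test the late session differs. Such statements have meaning here: T0 is the fasting value, and T30 enters the corrected insulin response and, through it, the disposition index. The AUC, insulin sensitivity, corrected insulin response and disposition index comparisons are separate analyses, and this point does not affect them.

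**Working it through.** The plan gives no error rate or power for these tests, so there is no stated figure to reproduce.

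**Inputs from the SAP.** 750 pairs (section 6); five times and two analytes (section 7); omnibus test, then unadjusted paired t-tests (section 8).

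**Assumptions, not in the documents.** Two-sided alpha 0.05 at both steps. Late-minus-early differences correlated 0.4, 0.6 or 0.8 between adjacent times, decaying with distance. Analytes independent unless stated. True differences of 0.5 SD (one real point) or 0.3 SD (two or three real points).

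**Step 1: upper bounds with independent tests.** With one real time point, four nulls remain per analyte.
- One analyte: 1 − 0.95^4 = 18.5%.
- Both analytes: 1 − 0.95^8 = 33.7%.

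**Step 2: simulation with correlated differences.** The table shows the chance of at least one false time-point claim per analyte when the omnibus test is the joint test of condition and condition-by-time. An interaction test gives practically the same figures.

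| Times that truly differ | Null times | r = 0.4 | r = 0.6 | r = 0.8 |
|---|---|---|---|---|
| T120 | 4 | 17.3% | 15.7% | 12.6% |
| T90, T120 | 3 | 13.4% | 12.3% | 10.2% |
| T60 to T120 | 2 | 9.3% | 8.8% | 7.8% |
| T30 to T120 | 1 | 5.0% | 5.0% | 5.0% |

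**Step 3: condition main effect as the omnibus test.** With T120 alone different by 0.5 SD, the overall rates are 16.7%, 12.9% and 7.1%. They are lower because a difference at one time is diluted in the average and the test is not always significant. At 0.3 SD they are 10.2%, 8.1% and 6.3%.

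**Step 4: both analytes.** With the same pattern in each, the rate is 1 − (1 − p)².
- One null point: 1 − 0.95² = 9.75%.
- Four null points, r = 0.8: 1 − 0.874² = 23.6%.
- Four null points, r = 0.4: 1 − 0.827² = 31.6%.

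Correlation between analytes lowers these slightly. In a setting with equal correlation 0.7 across times, a between-analyte correlation of 0.3 to 0.5 takes 24.4% to 23.9–22.7%.

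**Step 5: no difference at any time.** If one condition effect is the omnibus test, the overall false-claim rate is 1.9–5.0% per analyte (equal correlations 0.3 to 0.7), so the first step does its job. If either the main effect or the interaction may qualify, each at 0.05, it is 6.6–8.1%. If the time effect alone may qualify, the first step gives no protection, because glucose and insulin change over time after any 75 g load; five unprotected null tests give about 15–21%.

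**Step 6: with Holm.** With T120 alone different, Holm within analyte gives 3.5–4.7% per analyte. With one null point it gives 5%. Over two independent analytes it allows up to 1 − 0.95² = 9.75%. Holm over all ten tests gives 3.6–4.7% in the T120 setting.

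**Step 7: cost in power.** Difference detectable with 80% power in 750 pairs, in SD of the paired difference:
- Alpha 0.05: (1.960 + 0.842)/√750 = 0.102.
- Alpha 0.01 (first Holm step, five tests): (2.576 + 0.842)/√750 = 0.125.
- Alpha 0.005 (first Holm step, ten tests): (2.807 + 0.842)/√750 = 0.133.

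**The case against.** The strongest reply is that the size of the problem depends on things the documents do not give. A difference at T120 alone, exactly zero elsewhere and repeated in both analytes, is close to the worst case. A late-session effect that spreads over several times leaves fewer nulls, and with one null left the rate is the nominal 5%. This stands, and it is why the result is given as a range.

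A second reply is that the t-tests are conditional follow-ups beside the AUC and index comparisons, and that the SAP never calls them confirmatory. This stands in part. The SAP does not call them exploratory either, and it says their purpose is to test significance at each time. Labelling them exploratory would also settle the matter.

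A third reply is that Holm controls error without any preceding ANOVA. This is correct: the ANOVA may stay as the overall comparison, but the adjustment provides the protection.

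A reader might go further and infer that all five t-tests per analyte carry a 13–18% error rate as a fixed property of the plan. The documents do not support that. If a real difference produced the significant ANOVA, at most four of the five tests are null. Five nulls would be tested routinely only if a time effect alone sufficed. The SAP does not exclude that in words, but it is a strained reading of an ANOVA whose stated use is to compare the two sessions.

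**Conclusion.** The plan as written controls the time-point error rate only when the sessions differ at no time. Under the stated assumptions, the chance of at least one false time-point claim per analyte runs from 5% (one null point) to about 13–17% (four null points, joint or interaction test). With the condition main effect as the omnibus test and a 0.5 SD difference at T120, it is about 7–17%. Over both analytes the range is about 10% to 32%, and the upper part needs four null points in each.

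An inflation to about three times nominal is therefore the upper part of the range and should not be taken as the expected value. The defect itself does not depend on those assumptions: no adjustment is named, and the qualifying ANOVA effect is left open. It should be corrected, but it concerns follow-up tests and leaves the other analyses in section 8 intact.

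**What to change.** In SAP section 8, replace the sentence on paired t-tests with text that does three things:

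- States a two-sided significance level of 0.05.
- States that the ANOVA effect leading to time-point comparisons must involve condition (the condition effect or condition-by-time, named in advance) and that an effect of time alone does not qualify.
- Reports the early-versus-late comparisons at the five times with Holm-adjusted p-values: within analyte if claims are made separately for glucose and insulin, or over all ten tests if one study-wide error rate is claimed. Within-analyte Holm still allows up to about 10% over both analytes, so the choice should match the claim.

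If the sponsor regards the time-point tests as descriptive, labelling them exploratory and making no significance claims from them is an acceptable alternative.

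The change needs no new data. Its cost is some power at the strictest step: the detectable difference in 750 pairs rises from 0.102 to 0.125 SD within analyte, or to 0.133 SD over all ten tests.
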